## **6.4. Handling of Missing Data**

Subjects who discontinue the study prior to or after the initiation of the study drug will not be replaced and available data for these subjects until the point of discontinuation will be summarized.

The missing baseline assessment will not be imputed.

For categorical variables with missing values, a category documenting the frequency of missing values will be displayed in the summary tables.

Subjects who discontinue early will be encouraged to have all Day 71 procedures and assessments completed at an early termination visit.

There will be no imputation of missing values for safety data, however missing relationship between AE and study drug will be considered as related to study drug following worst case principle. Missing severity of an AE will be summarized as a severe AE.

Immunogenicity samples with a positive titer value will undergo a log transformation for analyses. Samples with titer level less than 1 will be assigned or imputed as a log transformed titer of zero (0) for analyses.

### **6.4.1. Imputation of Partial Dates**

#### **6.4.1.1. TEAE Status for Completely Unknown Start Date**

The following rules will apply in cases where start date of an AE is completely unknown:

- If the AE onset date is unknown and the end date is after first injection on Day 1 or ongoing, then the AE will be considered a TEAE.
- If the AE onset date is unknown and the end date is before first injection on Day 1, then the AE will not be considered a TEAE.
- If both the start and end dates are unknown (or end date is ongoing), then the AE will be considered a TEAE, following the worst-case principle.

If the AE onset date is partly present and month/year is prior to the first injection date then the AE will not be considered a TEAE.

#### **6.4.1.2. Concomitant Status of Medication for Completely Unknown Start Date**

The following rules will apply in cases where start date of concomitant medication is completely unknown:

- If the medication onset date is unknown and the end date is after first injection on Day 1 but before the last injection date or medication is ongoing, then the medication will be considered as concomitant.
- If the medication onset date is unknown and the end date is before first injection on Day 1, then the medication will not be considered as concomitant.

- If both the start and end dates are unknown, then the medication will be considered as concomitant. This approach is considered to be the most conservative following the worst-case principle.

If the medication onset date is partly present and month/year is prior to the first injection date, then the medication will not be considered as concomitant.

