17.6.1. Prior, Concomitant, and Follow-up Medication

The World Health Organization (WHO) Drug Dictionary will be used to classify prior and concomitant medications by therapeutic class. Prior medication will be defined as any medication taken prior to the first dose of study drug. Concomitant medication is defined as any medication taken between the date of first dose of study drug and the date of last dose of study drug. Any medications started after the last dose of study drug will be considered as follow-up medications.

Prior, concomitant and follow-up medication use will be summarized descriptively by the number and percentage of subjects in for each preferred term (generic name from WHO dictionary) by treatment arm. Multiple use of the same medication by a subject will be counted only once.

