#### **4.3. Prior Concomitant and Follow-up Medications**

All medications will be coded using World Health Organization (WHO) Drug Dictionary - Global B3 format 2018, by active ingredient and WHO anatomical therapeutic chemical (ATC) classification of ingredients.

A prior medication is defined as any medication taken prior to the first injection of the study drug.

A concomitant medication is any medication taken between the date of first injection of the study drug and the date of last injection of study drug or the medication is reported as ongoing. Any medications started after the last injection of the study drug will be considered as follow-up medications.

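### The SAP's partial-start-date rule classes medications still in use after first injection as not concomitant, contradicting the SAP's and protocol's own definitions

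*SAP*

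**What the plan says.** SAP 4.3 defines status by use: "A concomitant medication is any medication taken between the date of first injection of the study drug", with the window closing at the last injection. It adds a second route, "or the medication is reported as ongoing". Protocol 17.6.1 has the same window without the ongoing clause: "Concomitant medication is defined as any medication taken between the date of first dose of study drug and the date of last dose". Neither definition refers to when the medication was started. SAP 4.3 defines a prior medication as one taken before first injection, so one drug can be both prior and concomitant.

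SAP 6.4.1.2 deals with incomplete dates. For a completely unknown start it uses the end date. A drug that ended after first injection but before the last is concomitant, and so is an ongoing one ("or medication is ongoing, then the medication will be considered as concomitant"). A drug that ended before first injection is not. If both dates are unknown the drug is concomitant, with the reason "This approach is considered to be the most conservative following the worst-case principle".

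The section then closes with the rule that denies concomitant status when the start is partly known and early: "If the medication onset date is partly present and month/year is prior to the first injection date, then the medication will not be considered". No condition on end date or ongoing status is attached.

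SAP 7.6 reports prior, concomitant and follow-up medications by treatment arm and region, with a subject listing.

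**The concern.** Whether a drug was in use during the injection period depends on when it stopped, once it is known to have started earlier. The closing sentence of SAP 6.4.1.2 ignores the stop date. A drug recorded as started in June 2015 and still being taken is therefore declared not concomitant. The same drug would be concomitant with a full start date, and also with no start date at all. Knowing more about the start reverses the answer, although use during treatment is equally certain in all three cases. The sentence also runs against the worst-case principle stated just before it.

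At stake is the accuracy of a by-arm safety-context table. A programmer who follows the sentence will produce counts that do not meet the definition given in SAP 4.3.

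**Working it through.** The plan gives no figure to reproduce, so the check applies the two sets of rules to the same histories.

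**Inputs.** The definition in SAP 4.3 and the date rules in SAP 6.4.1.2. The dates are illustrative: first injection 10 October 2018 and last injection 21 November 2018, which is 42 days later and so matches Day 1 and Day 43.

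**Rules as logic.**
- SAP 4.3: concomitant if ongoing, or if start ≤ last injection and end ≥ first injection.
- SAP 6.4.1.2, unknown start: concomitant if ongoing, or if first injection < end < last injection; not concomitant if end < first injection.
- SAP 6.4.1.2, partial start: not concomitant if the start month/year is before that of first injection.

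All four drugs start before the month of first injection.

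| History | SAP 4.3 on true dates | 6.4.1.2, start unknown | 6.4.1.2, start partial |
|---|---|---|---|
| Started March 2015, ongoing | concomitant | concomitant | **not concomitant** |
| Started June 2018, ended 1 November 2018 (between injections) | concomitant | concomitant | **not concomitant** |
| Started June 2018, ended 1 December 2018 (after last injection) | concomitant | no rule applies | **not concomitant** |
| Started June 2018, ended 1 September 2018 (before first injection) | not concomitant | not concomitant | not concomitant |

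With a full start date, SAP 4.3 applies directly and there is no conflict. With a partial start, three of four histories conflict with SAP 4.3; only the drug that stopped before first injection agrees. Protocol 17.6.1 gives the same answers as SAP 4.3 here, because each of the first three drugs was in use between first and last dose.

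The third row shows a second, smaller gap. An unknown start with an end date on or after the last injection matches none of the bullets.

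**Size of one error.** SAP 3.1 plans 6 subjects per region per arm, hence 12 per arm over both regions. One subject wrongly left out of a row of the concomitant table moves that row by 1/6 = 16.7 percentage points in a region-specific arm, or 1/12 = 8.3 points in the pooled arm. This assumes the planned numbers are reached and that the subject has no other qualifying record of the same active ingredient, since SAP 7.6 counts repeated use once.

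**With the corrected sentence.** Testing the end date or ongoing flag makes all four partial-start histories match SAP 4.3.

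**The case against.** The strongest case on the other side accepts the contradiction but says that little follows from it. Most of that stands.

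- **A reader might infer that long-term medication disappears from the report.** It does not. The rule touches only partial start dates. Drugs with a full start date follow SAP 4.3, and ongoing drugs with a completely unknown start are kept. An affected drug still meets the prior definition, so it stays in the prior part of the SAP 7.6 summary and in the listing. SAP 6.1 also has all eCRF data listed.
- **A reader might infer that prohibited anticoagulant or antiplatelet use would be hidden, and with it a cause of bruising.** The documents do not support this. Exclusion criterion 6 bars subjects who require such drugs during the study or received them within 7 days before injection, apart from low-dose aspirin. SAP 4.2 names unmet entry criteria and prohibited medication among the deviation types, taken from eCRF data and monitoring reports, and SAP 7.2 lists every deviation. None of this is said to depend on the concomitant label.
- **A reader might infer bias in the comparison of techniques.** No planned analysis uses concomitant status. SAP 6.2 has no covariate adjustment, the model in SAP 7.7.1.1 contains only arm, visit and their interaction, and the bruise measurements in SAP 7.8.7 are summarised descriptively.
- **A number of affected subjects is tempting to give.** The documents contain no rate of partial dates or of long-term medication use, so any count would be a guess.

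It could also be argued that SAP 4.3 settles the matter because it already covers ongoing use. That does not stand. The SAP states no order of precedence, the sentence in 6.4.1.2 is the specific rule for partial dates, and Table 13 does not list it as a change from the protocol.

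**Conclusion.** The point holds as an internal contradiction with a limited effect. Followed as written, SAP 6.4.1.2 misclassifies any medication with a partial start month/year before first injection that is ongoing or ended on or after first injection. Such drugs are under-counted in the concomitant summary by arm and region. They are mislabelled in one summary and not lost from the report, and no estimate, confidence interval, test or adverse event count changes.

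The conclusion rests on reading the sentence literally; nothing elsewhere in the SAP or protocol modifies it. How many records are affected is unknown from the documents. The percentage-point figures describe one subject in one table row, not an expected error. The change is still worth making, because a reported table would otherwise contradict its own definition.

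**What to change.** Replace the closing sentence of SAP 6.4.1.2 with: *If the partial start date is before first injection, the medication is prior; it is also concomitant if it is ongoing, its end date is on or after the date of first injection, or its end date is unknown.* Treating an unknown end date this way follows the worst-case principle the section already uses.

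For a completely unknown start date, add that an end date on or after the last injection also makes the medication concomitant. State this as a worst-case convention, because such a drug could have started after the last injection and would then be a follow-up medication under SAP 4.3.

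While the section is open, the sponsor may also add rules for cases it leaves without one: a start known only to the month of first injection, a year-only start in the year of first injection, and partial end dates.

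The cost is one replaced sentence, one added clause and a small programming change. No new data are needed.

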#### **6.4.1.3. Missing EFP Onset Date**

Missing EFP onset days will be imputed with the first day of the month and missing onset month will be imputed with January. If the EFP onset date is indicated as completely unknown but starting less than 5 years ago, the EFP onset date will be imputed as the informed consent date minus 5 years. If the EFP onset date is indicated as completely unknown but starting more than 5 years ago, the EFP onset date will not be imputed. Missing EFP medication/treatment end days will be imputed with the last day of the month and missing end months will be imputed with December, except if the end year is equal to the date of injection year and then the EFP medication/treatment end date will be imputed with the first injection date.

### **6.5. Interim Analyses**

No interim analysis is planned in this study.

## **7. STATISTICAL ANALYSES**

### **7.1. Subject Disposition**

The number of subjects included in each study population will be summarized by treatment arm and by treatment region (ie, Buttocks, Thighs, and Overall). Subjects excluded from the safety or evaluable populations will be listed.

The number and percentages of subjects screened, completed, and discontinued during the study and study treatment, as well as the reason for discontinuation from study and reason for discontinuation of study drug will be summarized by treatment arm.

A listing of disposition data will be provided. Screen failure reasons will also be presented.

### **7.2. Protocol Deviation**

Protocol deviation will not be summarized. A listing of all protocol deviations will be presented.

### **7.3. Demographics and Baseline Characteristics**

Demographics and baseline characteristics will be summarized by treatment arm and by treatment region (ie, Buttocks, Thighs, and Overall) using the Safety Population. Age, height (at screening), body weight (at screening) and body mass index (BMI) in kg/m^2 will be summarized as continuous variables using descriptive statistics.

Gender, race and ethnicity will be summarized as categorical variables using frequency counts and percentages.

Refer to [Table 12](#) for descriptions of age categories and BMI groups.

The following baseline characteristics will be summarized using frequency counts and percentages:

- CR-PCSS cellulite severity ratings at screening (Mean and SD will also be provided)
- Hexsel CSS (B) depression depth scale scores at screening (Mean and SD will also be provided)
- Skin category based on Fitzpatrick scale assessment
- Report of tobacco and alcohol use
  - Alcohol use (Never, Current, and Former)
  - Tobacco use (Never, Current, and Former)

All demographic and baseline characteristics will be presented in subject listings.

#### **7.4. Medical and Surgical History**

Medical history will be coded using MedDRA dictionary. The version to be used will be defined in DMP. Medical and surgical history data will not be summarized; however, a subject listing will be provided.

#### **7.5. EFP History**

EFP history will be summarized by treatment arm and by treatment region (ie, Buttocks, Thighs, and Overall) using counts and percentages which will include:

- Family history of cellulite (Yes/No)
- Age (years) at EFP symptom onset (summarized descriptively)
- Prior treatments for EFP including liposuction, laser, massage, radiofrequency, drug, mesotherapy, cream, other, or none. Subjects can report more than 1 prior EFP treatment.
- Number of prior EFP treatments (0, 1, 2, or  $\geq 3$ )
- Time (years) since most recent EFP treatment (summarized descriptively)

Refer to [Table 12](#) for computation of “age at EFP onset” and “time since last EFP treatment.” EFP history will be listed.

#### **7.6. Concomitant Medications and Procedures**

The prior, concomitant and follow-up medication will be summarized by treatment arm and by treatment region (ie, Buttocks, Thighs, and Overall) using frequency counts and percentages by active ingredient within each ATC, with ATC and active ingredients ordered alphabetically. Multiple use of the same medication by a subject will be counted only once.

A subject listing of medications indicating prior, concomitant and follow-up medications and procedures will be provided. Similarly a separate listing of medications and procedures for EFP/ Cellulite will also be presented.

## **7.7. Efficacy Analyses**

Efficacy parameters will be summarized and analyzed for each treatment area by treatment arm using the Evaluable Population.

### **7.7.1. Improvement in Aesthetic Appearance using 3-D Photographic Images**

#### **7.7.1.1. Analysis of Treatment Region and Area**

The Likert Scale score of improvement in aesthetic appearance from baseline will be analyzed using a linear mixed model with treatment arm, study visit, interaction of treatment arm and study visit as fixed effects. The fixed effect estimates and 95% CIs for interaction effect of treatment arm and study visit will be presented. This model will be fitted using the response for each treatment area (ie, left buttock, right buttock, left thigh, and right thigh) and for the average of left and right of treatment area (ie, average of left buttock and right buttock; average of left thigh and right thigh).

The Likert Scale rating of improvement in aesthetic appearance from baseline will also be summarized using count and percentage by treatment arm and study visit/day (Day 22, 43, and 71) for each treatment area and with mean and SD.

A listing of Likert Scale scores will be provided.

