17.5. Efficacy Analyses

The efficacy endpoints for this study will include:

- Change from baseline in the blinded assessor's Likert Scale score of aesthetic appearance in each treatment area (buttocks or thighs) at Days 22, 43, and 71 by each treatment arm.
- Change from baseline in dimple depth and volume in each treatment area (buttocks or thighs) Days 22, 43, and 71 by treatment arm.
- Change from baseline in the Hexsel CSS (B) depression depth scale at Days 22, 43, and 71 by treatment arm.

The central assessor Likert Scale score of aesthetic appearance improvement from baseline in the 3-D photographic image, change from baseline in the Hexsel CSS (B) depression depth scale, and change from baseline in dimple volume and depth will be summarized by treatment arm and study visit using appropriate descriptive statistics. In addition, a linear mixed model will be utilized to fit change from baseline of each endpoint with treatment arm, cellulite dimples, and study visit as fixed effects, subject as random effect, and assessments across study visits as repeated measure. The fixed effect estimates and the corresponding 95% confidence intervals will be presented for each endpoint.

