**6. STATISTICAL METHODS**

**6.1. General Methodology**

All statistical tests, summary tables and data listings will be prepared using SAS version 9.4

All statistical tests of efficacy parameters will be two-sided with a significance level of  $\alpha=0.05$ , unless specified otherwise. Statistical tests will be supported by presenting estimates and 95% confidence intervals (CI) for the respective treatment effects. These estimates and CI will be based on the linear regression model.

Continuous data will be summarized using descriptive statistics. Discrete data will be summarized using frequency counts and percentages. The denominator will be based on the number of subjects in the appropriate population.

For the purpose of display, the summary results will be rounded as follows:

- Minimum and maximum: same number of decimal places as the raw data.
- Mean and Median: one more decimal place than the raw data.
- SD: Two more decimal places than the raw data.
- Percentages will be displayed with one decimal place precision. A zero count will be left blank.
- The standard form of a percentage change variable is 0 decimal place.

For categorical variables with missing values, a category documenting the frequency of missing values will be displayed in the summary tables.

Summary tables, subject listings, graphs and any supportive SAS output will include footnotes that will indicate:

- Date of data extraction
- Date and time of output generation
- SAS program name, including the path, that generated the output

When calculating percentages, the denominator will be based on the number of subjects with non-missing values. If the denominator is expected to change over time, then the denominator used to calculate the percentage will be based on the number of subjects with non-missing values at each visit. Any subject removed from an analysis will be noted at the bottom of the table along with the reason the subject was removed.

Empty summary tables will be presented with a note stating that “No Subjects Met Criteria.”

Subject listings of all data from the eCRFs as well as any derived variables will be presented.

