## 8. CHANGE FROM PROTOCOL

This SAP is prepared based on the original study protocol dated June 27, 2018 and the amended protocol dated August 29, 2018. There are no planned changes either in the conduct of the study or planned analysis at the time of preparing this SAP.

Table 13 lists any significant changes in the SAP from what is proposed in the protocol.

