**Table 13: Changes from Protocol**

Text in Protocol	Change in SAP	Justification
a linear mixed model will be utilized to fit change from baseline of each endpoint with treatment arm, cellulite dimples, and study visit as fixed effects, subject as random effect, and assessments across study visits as repeated measure. The fixed effect estimates and the corresponding 95% confidence intervals will be presented for each endpoint.	The Likert Scale score of improvement in aesthetic appearance from baseline will be analyzed using a linear mixed model with treatment arm, study visit, interaction of treatment arm and study visit as fixed effects. The fixed effect estimates and 95% CIs for interaction effect of treatment arm and study visit will be presented. This model will be fitted using the response for each treatment area (ie, left buttock, right buttock, left thigh, and right thigh) and for the average of left and right of treatment area (ie, average of left buttock and right buttock; average of left thigh and right thigh).	Clarify the same model will fit to the response for each treatment area. Remove the covariate of cellulite dimples from the model as the number of dimples treated is not play an role

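### The SAP restates the efficacy mixed model without its within-subject terms and specifies no confidence interval for a difference between injection techniques

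*SAP*

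**What the plan says.** Protocol 17.5 sets out a linear mixed model for each efficacy endpoint, with arm, cellulite dimples and visit as fixed effects and "subject as random effect, and assessments across study visits as repeated measure".

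SAP 7.7.1.1 says the Likert score "will be analyzed using a linear mixed model with treatment arm, study visit, interaction of treatment arm and study visit as fixed effects". It lists no random effect, repeated factor, covariance structure or degrees-of-freedom method. On output it says: "The fixed effect estimates and 95% CIs for interaction effect of treatment arm and study visit will be presented". The model is fitted to each treatment area and to the left-right average. Sections 7.7.2 (dimple volume and depth) and 7.7.3 (Hexsel) refer back to it, so every modelled efficacy endpoint depends on this wording.

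SAP Table 13 sets the protocol model beside the SAP model. Its justification has two parts: "Clarify the same model will fit to the response for each treatment area" and "Remove the covariate of cellulite dimples from the model as the number of dimples treated is not play an role". Neither concerns the subject or repeated-measures terms. The text above the table says: "There are no planned changes either in the conduct of the study or planned analysis at the time of preparing this SAP".

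SAP 6.1 adds: "Statistical tests will be supported by presenting estimates and 95% confidence intervals (CI) for the respective treatment effects", and then "These estimates and CI will be based on the linear regression model".

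**The concern.** Three things are left open.

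- **The model.** The SAP calls it mixed in 7.7.1.1 and 7.7.2 and a linear regression in 6.1, and omits the terms that would make it mixed. One programmer could add a subject effect from the protocol. Another could fit the listed fixed effects and treat a subject's three visits as independent. Their intervals would differ.
- **The contrast.** The primary objective is to assess treatment effects by injection technique. An interaction effect, with no reference arm or visit named, does not measure that. The treatment effects mentioned in 6.1 are not defined.
- **The dimples (7.7.2 only).** SAP 3.9 traces dimples individually. Table 1 gives two per treatment area and 3.5.1 at least two. No rule says how they become one value per area before modelling.

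At stake is how the five techniques are compared. The study is exploratory, so no confirmatory decision depends on it.

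**Working it through.** **Inputs from the documents.** Five arms, 6 subjects per arm per region (SAP 3.1), efficacy visits at Days 22, 43 and 71 (SAP 4.5.1), two-sided 5% level (SAP 6.1). The planned size reproduces: 5 × 6 × 2 regions = 60. No SD, correlation, power or precision is stated.

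**Assumptions.** Total SD 1 at each visit, the same correlation ρ between any two visits of a subject, complete data, ρ = 0.3, 0.5 or 0.7.

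**Degrees of freedom, one treatment area.** There are 5 × 6 × 3 = 90 rows and 15 arm-by-visit means. The independence fit has 90 − 15 = 75 df (t = 1.992). A comparison on subject-level values has 5 × (6 − 1) = 25 df (t = 2.060).

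**Standard errors for two arms, in SD units.**

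| Contrast | Independence fit | With correlation ρ |
|---|---|---|
| Interaction (change in the arm difference between two visits) | √(4/6) | √(4(1−ρ)/6) |
| Arm difference averaged over three visits | √(2/18) | √(2(1+2ρ)/18) |
| Arm difference at one visit | √(2/6) | √(2/6) |

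The independence fit overstates the interaction SE by 1/√(1−ρ) = 1.20, 1.41, 1.83. Its SE for the visit-averaged difference is 1/√(1+2ρ) = 0.79, 0.71, 0.65 of the correct one.

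**95% half-widths and simulated coverage of the independence fit** (ρ = 0.3 / 0.5 / 0.7).

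| Contrast | Independence half-width | Correct half-width (25 df) | Coverage, independence fit |
|---|---|---|---|
| Interaction | 1.992 × √(4/6) = 1.63 | 1.41 / 1.19 / 0.92 | about 98% / 99.3% / 99.9% |
| Visit-averaged difference | 1.992 × √(2/18) = 0.66 | 0.87 / 0.97 / 1.06 | about 88% / 83.5% / 79% |
| Single-visit difference | 1.992 × √(2/6) = 1.15 | 1.19 | 94.5% to 95% |

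A random-intercept model uses 50 within-subject df for the interaction, which gives 1.37 / 1.16 / 0.90 instead of 1.41 / 1.19 / 0.92. In simulation, restoring only the subject random effect gave 94.9% to 95.1% coverage for all three contrasts.

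**What the interaction shows.** Take one arm 1 point better than the others at all three visits. In a reference-coded fit every interaction coefficient is 0 and the 1 point is in the arm coefficient, whose interval 7.7.1.1 does not list. If the interaction effect is read instead as the arm-by-visit means, there is an interval for each arm but still none for a difference between arms.

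**Dimples (7.7.2).** If two dimples per area entered as independent rows (180 rows, 165 df), the single-visit arm difference would also be affected. Coverage would be about 91%, 89% and 87% at assumed between-dimple correlations of 0.3, 0.45 and 0.6. Averaging the dimples first gives 94.9% to 95.2%.

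**The case against.** The strongest reply is that the independence fit is the least natural reading. The SAP calls the model mixed, listing fixed effects describes only the fixed part, Table 13 reproduces the protocol's terms, and section 8 says no change of analysis is planned. The regression sentence in 6.1 is generic. This has force: the within-subject terms may well be intended. It does not settle the matter, because the word mixed does not say which random or repeated terms apply. The statement of no planned change stands above a table that lists a model change.

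A second reply is that the poorest coverage belongs to a visit-averaged difference that the SAP never asks for by name. For the interval it does name, the error is conservative, and a single-visit difference is almost unaffected. That is correct. The 79% to 88% figures apply only if visits are treated as independent and the treatment effects of 6.1 are read as averages over visits. The dimple figures likewise need separate dimple rows, whereas SAP 7.7 leans towards one value per area.

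A third is that the objective names no comparison, 7.7.1.1 also gives descriptive summaries by arm and visit, and the table layouts are in SAP Module 2, which was not supplied. Differences may be displayed there, so the point is limited to the SAP text. Descriptive summaries still give no interval for a difference between techniques.

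**Conclusion.** The concern holds and should be fixed. The omission of the protocol's within-subject terms, the lack of any justification for it, the conflict with 6.1 and the absence of a specified between-technique interval can all be read directly from the text. They do not show that correlation will be ignored; they show that the SAP permits it.

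If it were ignored, interaction intervals would be about 1.2 to 1.8 times too wide. Intervals for visit-averaged arm differences would have a half-width of 0.66 SD where 0.87 to 1.06 SD is correct. Single-visit differences with one row per subject would be essentially right. These sizes rest on assumed correlations of 0.3 to 0.7, equal variances and complete data. The missing technique contrast does not depend on those assumptions.

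**What to change.** - **SAP 7.7.1.1 and Table 13:** state that visits are repeated within subject, and give the covariance structure and a small-sample degrees-of-freedom method such as Kenward-Roger. A subject random intercept is enough under equal variances; an unstructured covariance with a simpler fallback is a reasonable alternative. Record any departure from the protocol wording, with its reason, in Table 13.
- **SAP 6.1:** replace the reference to linear regression with this model, and define the treatment effects.
- **Output:** in place of, or alongside, the interaction coefficients, present least-squares means by arm and between-arm differences with 95% intervals at Days 22, 43 and 71.
- **SAP 7.7.2:** average the target dimples within each treatment area before modelling, or add a dimple-within-subject effect.

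The cost is SAP wording and a few lines of code, with no new data. Compared with an independence fit, intervals for visit-averaged differences become wider and those for interactions narrower.
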